SECONDARY OBJECTIVES	To evaluate rates of late (> 3 months after treatment) gastrointestinal toxicity following fractionated Linac based SBRT for pancreatic tumors. Toxicities of note include grade 2 or greater gastritis, enteritis, fistula, or ulcer and any other grade 3 or greater gastrointestinal toxicity. To evaluate local progression free survival, overall survival and metastasis-free survival rates after Linac based SBRT and subsequent resection in patients with resectable and/or borderline resectable pancreatic adenocarcinoma of the head and/or body. To develop and standardize Linac based SBRT delivery and dosimetric parameters. To estimate resection margin positivity (R0/R1) and pathologic complete response rate after neoadjuvant SBRT To evaluate pre- and post- SBRT patient reported quality of life (QOL)
TREATMENT	After 3- 4 months of chemotherapy, patients will be enrolled to a single arm trial of stereotactic body radiotherapy (SBRT) in 5 fractions given over 15 days. They will then proceed to surgery after a break of 4-6 weeks.

INCLUSION CRITERIA	
 • Age >18 years. • Karnofsky Performance Status >70% (see Appendix IV). • Histologically confirmed pancreatic adenocarcinoma of the head and/or body; at least the majority of the histopathologic specimen must be identified as adenocarcinoma. • Pancreatic tumors must be considered at least borderline resectable and/or borderline resectable at time of treatment planning. Definition of resectable and/or borderline resectable: no metastases, less than 180 degree involvement of hepatic artery, superior mesenteric artery or celiac artery • No active infection requiring hospitalization • If bilirubin > 2, patients must have a biliary stent placed prior to SBRT. • Patients must have acceptable organ and marrow function (see section “Inclusion Criteria, page 17-18). • Women who are not post-menopausal (as defined in Appendix V) should have a negative urine or serum pregnancy test. Women of childbearing potential must agree to use adequate contraception for the duration of study participation. • Ability to understand and the willingness to sign a written informed consent document. • Life expectancy > 3 months. • Patients are to have received neoadjuvant chemotherapy prior to enrollment. Approved regimens may consist of 3-4 months of gemcitabine-based chemotherapy or FOLFIRINOX. Patients will have a 2-4 week break between last chemotherapy administration and start of

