--------------------	--

EXCLUSION CRITERIA	
 • Presence of metastatic disease. • Infections requiring systemic antibiotic treatment. • Unable to understand or unwilling to sign a written informed consent document. •
PROCEDURES	Endoscopically guided fiducial placement with optional biopsies obtained at the time of fiducial placement.
STATISTICAL CONSIDERATIONS	See statistics section.

SCHEMA

Eligibility: resectable or borderline resectable adenocarcinoma of the pancreas. Definition of resectable: no metastases, less than 180 degree involvement of hepatic artery, superior mesenteric artery or celiac artery

I. OBJECTIVES

Primary Objective

- To evaluate rates of acute (within 3 months of treatment) grade 3 or greater gastrointestinal toxicity.

Secondary Objectives

- To evaluate rates of late (> 3 months after treatment) grade 2 gastritis, enteritis, fistula, and ulcer, or any other grade 3 or greater gastrointestinal toxicity
- To determine rates of local progression free survival, overall survival, and metastasis- free survival in patients with resectable and/or borderline resectable pancreatic adenocarcinoma of the head and/or body undergoing neoadjuvant SBRT
- To evaluate patient quality of life before and after Linac based SBRT.
- To evaluate the margin positivity rate and pathologic complete response rate after Linac based SBRT.
- To further develop standardization of Linac based SBRT delivery and dosimetric parameters.

II. BACKGROUND

Natural History and Management of Pancreatic Cancer

More than 40,000 individuals are diagnosed with pancreatic cancer annually in the United States. Despite aggressive combined modality treatment approaches, five-year survival of patients with pancreatic cancer is still less than 5% (1). Clearly, more innovative treatments are needed to improve survival in this group of patients.

Surgical resection is considered to be the only potentially curative treatment option (2). However, the majority of pancreatic cancer patients do not have resectable and/or borderline resectable disease at presentation. More than 85% of patients have locally advanced or metastatic disease when initially diagnosed.

Current Adjuvant Management of Resectable and/or borderline resectable Pancreatic Adenocarcinoma

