The phase I feasibility study outlined in this protocol proposes a 6.6 Gy x 5 fractionation schedule treating the region of tumor plus a 3 mm margin. These volumes will be substantially smaller than the regimens outlined above for rectal and pancreatic cancer, likely leading to a lesser degree of toxicity. Using the linear-quadratic formulation, the biologically equivalent dose (BED) of the two proposed fractionation schedules are given in comparison to other commonly used schemes (table 1). The BED of the proposed 6.6 Gy x 5 schedule (BED early/late 54.8/105.6) closely approximates that of standard chemoradiation (BED early/late 60/83.3), but without concurrent chemotherapy and treating (0.3 cm vs. ~2 cm). Furthermore, the proposed 6.6 Gy x 5 fractionation schedule has a much lower late BED (105.6 vs. 233.3) with a similar early BED (54.8 vs. 87.5) as the previous 25 Gy x 1 regimen that has resulted in higher toxicity.

Table 1:

	Nodes Tx	Concurrent Chemo	BED early	BED late
			a/b=10	a/b=-3
50.4	Yes	5-FU	60	83.3
30 Gy/10	Yes	Gemcitabine	39	60
25 Gy/5	No	No	37.5	66.7
33 Gy/5	No	No	54.8	105.6
25 Gy/1	No	No	87.5	233.3

In this study, we will refine our current understanding of radiation tolerance of the pancreas and adjacent organs, thereby making it possible to treat future patients more safely and aggressively.

The major benefit of Linac based SBRT/chemotherapy for resectable and/or borderline resectable pancreatic tumors is improved local control from improved sterilization of primary tumor and lymph nodes, and well as faster delivery with lower side effects. In addition, radiosurgical ablation of the tumor at the primary site early after diagnosis can theoretically prevent distant seeding from the pancreatic tumor itself. Ultimately, these improvements in the treatment of pancreatic cancer may translate into an improved quality of life and overall survival.

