Quality of life will be assessed using the European Organization for Research and Treatment in Cancer quality of life core cancer questionnaire with the pancreatic cancer module (EORTC QLQ-C30/PAN26). The EORTC QLQ-C30 is a multidimensional, 30-item questionnaire, which assesses five functional scales (physical, role, cognitive, emotional, and social), three symptom scales (fatigue, pain, and nausea/vomiting), a global health/QOL scale, as well as 6 single items (42). The EORTC QLQ-PAN26 supplements the core questionnaire with 26 items specific for patients with pancreatic cancer (43,44). These instruments have been validated in patients receiving treatment for metastatic and resected pancreatic cancer and are sensitive to identify treatment related changes in quality of life. The quality of life of patients in this study will be compared to historical cohorts of patients treated with conventional chemoradiation at University of Cincinnati and other institutions.

IV. METHODS

REGISTRATION PROCEDURES

General Guidelines

Subjects will be identified per the recommendation of Surgeons, Medical Oncologists, Radiation Oncologists or GI Combined Modality Tumor Board or equivalent combined modality assessment. Subjects will be recruited through self-referral and the advice of their attending physician. Patients will be enrolled prior to start of SBRT. Patients will have chemotherapy (3-4 months) for pancreas cancer prior to study enrollment.

Registration Process

A member of the research team (most likely the research coordinator) will enroll the patient into the trial. Consent will be obtained after a clear and thorough discussion between the patient and the principal investigator or any of the co-investigators in clinic. Any patients that are deemed by the principal investigator or co-investigators to be mentally or physically incapable of consent will not be included in the study.

SBRT ADMINISTRATION AND RADIATION TREATMENT PLANNING

Pre-Linac based SBRT Tests, Procedures, and Planning

The following will be completed prior to Linac based SBRT:

- Signed informed consent document.
- Medical history and clinical examination.
- CBC with differential, Chemistry Panel, CA19-9.
- Gold fiducial seed placement percutaneously, intraoperatively, or under endoscopic ultrasound guidance, technique will be determined clinically. Fiducial placement may be performed prior to enrollment.

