All late AE and the maximum grade for each type of adverse events (including all adverse events and those that are possibly, probably or definitely related to study treatments) will be recorded for each patient. The frequency tables will be reviewed to determine the patterns. Point estimate and confidence interval will be reported for binary endpoints. All patients meeting the eligibility criteria and confirmed by central review who have signed a consent form and have begun any dose of treatment will be evaluable for the following secondary endpoints, unless otherwise specified.

- The positive margin resection rate is defined as number of patients achieved R0 versus R1/R2 resection during surgery divided by number of evaluable patients. (R0= negative margin, R1= microscopically positive margin, R2= macroscopically positive margin). Point estimate and confidence interval of the rate will be reported.
- The histopathologic response rate is defined as number of patients achieved CR or PR determined according to histopathologic examination during pre-operative chemo or chemoradiotherapy divided by number of evaluable patients. Point estimate and confidence interval of the rate will be reported.
- Time to locoregional recurrence is defined as time from the date of registration to the date of the first documented locoregional recurrence. The Kaplan-Meier methods will be used to estimate the median time, and event-free rate at specific time points (6 month, 12 month, etc.).
- Time to distant recurrence is defined as time from the date of registration to the date of the first documented distant recurrence. The Kaplan-Meier methods will be used to estimate the median time, and event-free rate at specific time points (6 month, 12 month, etc.).
- Overall survival is defined as time from the date of registration to the date of the death due to all causes. The Kaplan-Meier methods will be used to estimate the median time, and event-free rate at specific time points (6 month, 12 month, etc.).

Safety Stopping Rules

In addition to toxicity feasibility stopping rules, accrual will be temporarily suspended to the study, if at any time, we observe events considered at least possibly related to study treatment an adverse event with attribute specified as ("possible," "probably," or "definite") that meet the following:

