Patients will be evaluated for anti-tumor effect by follow-up imaging (pancreas protocol CT and/or PET-CT imaging) as outlined above. All subsequent scans (post-treatment) will be compared to the same pretreatment CT that was used in conjunction with radiation treatment planning.

Patients will be evaluable for toxicity and evaluable for objective response at the follow-up intervals specified above.

Disease Parameters

Pancreatic tumor response will be based upon standard radiographic criteria for the treated lesion and will be prospectively recorded in the UC secure database. Radiographic response of the pancreatic tumor by diagnostic CT scans will be defined according to RECIST criteria as described below:

- CR = complete disappearance of index lesion
- PR = at least 30% decrease in the longest diameter of the index lesion
- PD = more than 20% increase in the longest diameter of the index lesion
- SD = does not meet criteria for PR or PD

Local tumor progression will be defined as $\geq20\%$ increased size on CT scan compared to a CT

scan from prior to treatment. Distant progression will be defined as any new tumor found outside of the pancreas or periampullary region on CT scan. Local and/or distant progression will be evaluated by both PET/CT (if available) and CT scan as deemed by treating physician.

Methods for Evaluation of Measurable Disease

Pancreas protocol CT scans (biphasic imaging, 1.25 mm cuts) and/or FDG PET-CT scans (optional and if recommended by the treating physician) will be obtained at all follow-up intervals as described in the treatment calendar.

XIII. RESPONSE CRITERIA

Evaluation of Target Lesions

Patients' responses to therapy will also be evaluated clinically after completion of their Linac based SBRT. The following are clinical definitions for response:

- CR = complete alleviation of pain or other symptoms thought to be related to the index lesion
- PR = improvement, but not complete elimination, of pain or other symptoms thought to be related to the index lesion
- PD = worsening of pain or other symptoms thought to be related to the index lesion SD = does not meet criteria for PR or PD
- Radiographic response will be defined as outlined in section 11.1.2.

Evaluation of Non-Target Lesions

Standard radiographic criteria will be utilized for non-target lesions. Any disease outside of the pancreas region will be considered metastatic disease. If possible a biopsy should be obtained to confirm metastasis.

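### Section IX ties histopathologic response to chemotherapy or chemoradiotherapy instead of SBRT, and so does not match the objective of pathologic complete response after SBRT

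*Combined protocol and SAP*

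**What the plan says.** **The definition.** Section IX, Supplementary Analysis Plans (Secondary Endpoints), takes the numerator of the histopathologic response rate as patients with CR or PR, "determined according to histopathologic examination during pre-operative chemo or chemoradiotherapy divided by number of evaluable patients". A point estimate and confidence interval are to be reported. Evaluable patients are those who are eligible on central review, have consented and have started any dose of treatment.

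**The objective.** The Synopsis gives it as "To estimate resection margin positivity (R0/R1) and pathologic complete response rate after neoadjuvant SBRT". Section I gives it as "To evaluate the margin positivity rate and pathologic complete response rate after Linac based SBRT".

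**The treatment.** Under Treatment in the Synopsis, "patients will be enrolled to a single arm trial of stereotactic body radiotherapy (SBRT) in 5 fractions given over 15 days", and "They will then proceed to surgery after a break of 4-6 weeks". Section IV, General Guidelines, says "Patients will have chemotherapy (3-4 months) for pancreas cancer prior to study enrollment". Section III describes the regimen as given "but without concurrent chemotherapy".

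**Response criteria elsewhere.** Section XII defines CR and PR radiographically, for example "PR = at least 30% decrease in the longest diameter of the index lesion". Section XIII adds definitions based on symptoms. Neither section gives a histopathologic definition.

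**The concern.** The endpoint rule and the objective it serves describe different things. The rule names two therapies, and neither is the treatment under study. It also pools partial with complete response, whereas both statements of the objective concern complete response only.

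Pathologic response is a large part of the case for this regimen: Section III cites encouraging pathologic results, including a 50% pathologic complete response rate among resected patients, as a reason for interest in it. If the analysis follows Section IX, the report may carry a pooled rate with an unclear treatment label, and the complete response rate promised in the objectives may not appear at all. A later phase II team would then have to reconstruct it from the pathology reports.

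**Working it through.** The documents attach no target, power or sample size to this endpoint, so there is no figure to reproduce. The check compares the relevant passages.

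1. **Does pre-operative chemo describe the study treatment?** No. Section IV places the 3-4 months of chemotherapy before enrolment, and the inclusion criteria in Section V add a 2-4 week break before SBRT starts.

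2. **Does chemoradiotherapy describe it?** Not as the protocol uses the term. Table 1 in Section III lists no concurrent chemotherapy for 33 Gy in 5 fractions. The same section sets the SBRT regimen against standard chemoradiation when comparing biologically equivalent dose, and plans to compare quality of life with historical cohorts given conventional chemoradiation. Section VI lists standard chemotherapy/radiation among the alternatives to taking part. In Section IX itself, the toxicity rule attributes events to SBRT by name.

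3. **When is the specimen available?** Surgery follows SBRT by 4-6 weeks. Appendix I schedules biopsy only at pre-study, and the optional core biopsies in Section IV go with fiducial placement, before SBRT. Response after SBRT can therefore be read only on the resection specimen. Section X already collects surgical pathology reports with staging, margin status and histology, but lists no regression grade.

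4. **Does the denominator matter?** Section III's 50% refers to 17 patients who went to resection. Section IX divides by all evaluable patients, resected or not. To show the effect, assume half of resected patients have a complete response and let the number resected out of 20 vary:

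| Resected | Complete responses | Rate among resected | Rate among 20 evaluable |
|---|---|---|---|
| 6 (minimum in the completion rule) | 6 × 0.5 = 3 | 3/6 = 50% | 3/20 = 15% |
| 8 (40% of 20) | 8 × 0.5 = 4 | 4/8 = 50% | 4/20 = 20% (exact 95% CI 5.7-43.7%) |
| 20 (all) | 20 × 0.5 = 10 | 10/20 = 50% | 10/20 = 50% (27.2-72.8%) |

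These counts are assumptions, not forecasts. They show only that a rate over all evaluable patients cannot be set directly beside a rate among resected patients.

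5. **Do other rules depend on the wording?** No. The completion rule counts therapy completed with R0 or R1 resection, not response. Its stated error rates reproduce: with X binomial on 20 patients, P(X ≤ 5) = 0.804 at a 20% rate (stated as more than 80%) and 0.126 at 40% (stated as less than 13%).

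**The case against.** The best defence is that the intent is plain. Both statements of the objective place the assessment after SBRT, and the surgical pathology reports are collected. The sentence can also be parsed so that the word *during* attaches to the response being achieved, with histopathology only the means of finding it. On that parse a resection specimen qualifies on timing. Chemotherapy is a required part of the sequence, and Section III once joins SBRT and chemotherapy in a single phrase, so naming chemotherapy is not absurd.

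Most of this stands. It disposes of the timing difficulty and keeps the severity low. It does not put SBRT into the definition, and it does not reconcile a pooled CR-plus-PR rate with an objective limited to complete response.

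Two further readings go too far:

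- A reader might infer that the CT or symptom criteria for PR would be applied to specimens. Sections XII and XIII label them radiographic and clinical, and Section IX asks for histopathology. The gap is only that pathologic PR is undefined.
- A reader might infer that this gap prevents comparison with the cited 50%. That figure is a complete response rate. What stands in the way is pooling CR with PR and the difference in denominators.

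**Conclusion.** The definition is wrong as written and should be corrected, at low severity. It rests on the ordinary meaning of chemoradiotherapy in this protocol; no passage extends that term to SBRT given alone. The effect is confined to one estimation-only secondary endpoint in a study of up to 20 patients.

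A reader might infer that the rule must return 0 responders out of 20, because no specimen is examined while chemotherapy or chemoradiotherapy is under way. The documents do not support that as an expected result: it requires the strictest parse and an analyst who ignores both statements of the objective.

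Nor can one estimate how many responders would be lost. The 40% resection rate in Section IX is the favourable value at which the completion rule's error is quoted, not a target. The 25 of 36 patients in Section XI who remained resectable come from a plasma-marker cohort in a different setting. The 50% response figure is a personal communication on 17 resections from a locally advanced or borderline series.

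**What to change.** In the histopathologic response item of Section IX:

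- Replace the reference to chemo or chemoradiotherapy with: *determined on the resection specimen after pre-operative chemotherapy and SBRT*.
- Define pathologic complete response as no viable tumor cells.
- Report the pathologic complete response rate on its own, with its confidence interval, over all evaluable patients and again over resected patients. The second rate is the one to set beside the resected-patient figure in Section III.
- If CR plus PR is kept as an additional rate, name the regression category that counts as PR before any specimen is read.
- Describe the result as response to the chemotherapy-plus-SBRT sequence, since a single-arm study cannot separate the two.

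The cost is one sentence and one extra reported rate. Pathology reports are already collected; a regression-grade field is needed only if the pooled rate is kept. Treatment, visits and sample size do not change.

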- Creatinine clearance >60 mL/min/1.73 m² for patients with creatinine levels above institutional normal
- Ability to understand and the willingness to sign a written informed consent document.
- Patients are to have received neoadjuvant chemotherapy prior to enrollment (3-4 months). Approved regimens may consist of 3-4 months of gemcitabine-based chemotherapy or FOLFIRINOX. Patients will have a 2-4 week break between last chemotherapy

administration and start of SBRT.

- Patient must be able to have fiducials placed. If not, the tumor must be posterior and adjacent to the aorta and treatment will only be permitted at the discretion of the Principal Investigator.

Exclusion Criteria

- Children (< 18 years) are excluded because pancreatic tumors rarely occur in this age group. Furthermore, treatment requires a great deal of patient cooperation including the ability to lie still for several hours in an isolated room.
- Uncontrolled intercurrent illness including, but not limited to, ongoing or active infection (or infections requiring systemic antibiotic treatment), symptomatic congestive heart failure, unstable angina pectoris, cardiac arrhythmia, or psychiatric illness/social situations that would limit compliance with study requirements.
- Pregnant and breastfeeding women are excluded as are women of child-bearing potential who are unwilling or unable to use an acceptable method of birth control (hormonal or barrier method of birth control; abstinence) to avoid pregnancy for the duration of the study treatment. Should a woman become pregnant or suspect she is pregnant while undergoing radiotherapy in this study, she should inform her treating physician immediately.
- Women who are not post-menopausal (as defined in Appendix V) and have a positive urine or serum pregnancy test or refuse to take a pregnancy test.

VI. RISK / BENEFIT

Risk Information

It is difficult at this time to predict with confidence the percentage rate of complications from the proposed Linac based SBRT treatment. However, it is reasonable to extrapolate from the current experience with radiotherapy in and around the pancreas. Based upon prior phase I and phase II studies, we anticipate that the toxicities associated with this treatment will be acceptable.

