APPENDIX I

STUDY CALENDAR

	Pre-Study	Pre-SBRT ⁸	SBRT Treatment ^{9,10}	Follow-Up ⁵ (Post-Radiation Treatment)					
				4-6 weeks	4 mos	6 ³ mos	9 mos	12 ³ mos	Yrs 2-5 Q 3-6 mos
Initial Consult	X								
Demographics	X								
History / Physical Exam	X			X	X	X	X	X	X
Informed consent	X								
Biopsy (confirmed adenocarcinoma)	X								
Labs: CBC, CMP, CA19-9		X ⁶		X	X	X	X	X	X
Post-op complication assessment (appendix 6)				X					
Negative Pregnancy Test ⁷		X							
Seed Placement (EUS, CT, intraoperatively)		X							
Simulation Scan		X							
Radiologic Evaluation (CT)		X		X ²	X	X	X	X	X
QoL Questionnaire		X		X	X ⁴	X	X ⁴	X	X
AE Evaluation	X			X	X	X	X	X	X
Research tubes		X		X ¹¹					

1 - CT pancreas or chest/abdomen/pelvis, as per treating physician, required pre- and post-SBRT.
 2 - If being reevaluated for resection, scans will be conducted at 4-6 weeks or as determined necessary by treating physician.
 3 - It is preferred that patients have the 6MFU and 12MFU evaluation and imaging at the treating institution. Other evaluations may be done at a local center however records must be submitted to SBRT treating facility.
 4 - QoL questionnaires may be completed and returned by mail if preferred.
 5 - Follow-up appointments have a +/- 30 day tolerance window. (ex. 6MFU may occur between 5-7 months)
 6 - Pre-SBRT labs should be done within 2 weeks prior to treatment.
 7 - Pregnancy test by urine or serum, for women who are not post-menopausal as defined in Appendix III.
 8 - Pre-SBRT procedures should be completed within 45 days of beginning treatment.
 9 - It is recommended that patients discontinue any chemotherapy one week prior to SBRT
 10 - Ideally all 5 fractions should be delivered Monday through Friday; however, treatment may be delivered over 2 weeks, as long as the patient receives at least 2 fractions per week.
 11- Pre-surgery

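### Overall survival and both recurrence endpoints are timed from registration but analysed only in patients who began SBRT, which biases them slightly but systematically upward

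*Combined protocol and SAP*

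**What the plan says.** Section IX, Supplementary Analysis Plans (Secondary Endpoints), gives three time-to-event endpoints the same origin:

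- "Overall survival is defined as time from the date of registration to the date of the death due to all causes"
- "Time to locoregional recurrence is defined as time from the date of registration to the date of the first documented locoregional recurrence"
- "Time to distant recurrence is defined as time from the date of registration to the date of the first documented distant recurrence"

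All three are to be summarised by Kaplan-Meier medians and event-free rates at 6 months, 12 months and so on.

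The paragraph introducing these definitions sets the analysis population: eligible patients "who have signed a consent form and have begun any dose of treatment will be evaluable for the following secondary endpoints, unless otherwise specified". None of the three definitions specifies a different set.

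Section IV (Registration Procedures) places enrolment before radiotherapy: "Patients will be enrolled prior to start of SBRT". Sections IV and V put the 3-4 months of chemotherapy before enrolment. Section V adds a 2-4 week break between the last chemotherapy dose and SBRT.

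**The concern.** The clock starts at one event and membership of the analysis set is decided at a later one. Anyone who dies in between is left out, and everyone who remains has, by selection, survived the gap. This is immortal-time bias, and its direction is known.

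The gap contains real selection points. Simulation and, where still needed, fiducial placement come before SBRT (Section IV). Resectability is judged at treatment planning (Section V). Metastatic disease is an exclusion (Synopsis).

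The Synopsis objective concerns outcomes after SBRT and subsequent resection, and follow-up visits are counted from radiation (Section IV; Appendix I). A registration clock therefore adds scheduling time to a result meant to describe treatment. The documents provide no landmark, left truncation or analysis of all registered patients that would correct this.

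**Working it through.** **Which treatment must be begun.** Chemotherapy is complete before enrolment, so every registered patient has already had it. The restriction has an effect only if the treatment meant is SBRT.

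**How each endpoint is affected.**

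- *Overall survival:* a patient who dies before the first fraction cannot be in the set, so the curve stays at 100% for as long as all patients are still waiting. This is strict.
- *Distant recurrence:* metastases found before SBRT make the patient ineligible, so they do not appear as events.
- *Locoregional recurrence:* the effect comes mainly from measurement. Section XII compares only post-treatment scans with the planning CT. Local growth that leaves the tumour borderline resectable would not by itself prevent SBRT.

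**Size for overall survival.** The plan gives no target rate, event count or power for these endpoints, so there is no stated figure to reproduce. Inputs:

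- Wait W: 14 and 28 days, an assumption taken from the 2-4 week break in Section V and valid if registration follows the last chemotherapy dose. In months, 14/30.4375 = 0.46 and 28/30.4375 = 0.92.
- Median survival: 13.9 months (Section III, locally advanced patients in the multi-institutional SBRT study), with 8 and 23 months as the range (Section II, neoadjuvant series). These are background figures, not design assumptions.
- Constant hazard: λ = ln 2 / median.

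Among patients who survive the wait, with the clock at registration,

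S_obs(t) = S(t)/S(W) = exp[−λ(t − W)],

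so the median rises by exactly W. For a 13.9-month median, λ = 0.0499 per month:

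- unbiased 12-month survival: exp(−0.0499 × 12) = 0.550
- W = 0.46: exp(−0.0499 × 11.54) = 0.562
- W = 0.92: exp(−0.0499 × 11.08) = 0.575

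| True median (months) | Wait (days) | Median as planned | 6-month OS, unbiased → planned | 12-month OS, unbiased → planned |
|---|---|---|---|---|
| 8 | 14 | 8.5 | 59.5% → 61.9% | 35.4% → 36.8% |
| 8 | 28 | 8.9 | 59.5% → 64.4% | 35.4% → 38.3% |
| 13.9 | 14 | 14.4 | 74.1% → 75.9% | 55.0% → 56.2% |
| 13.9 | 28 | 14.8 | 74.1% → 77.6% | 55.0% → 57.5% |
| 23 | 14 | 23.5 | 83.5% → 84.6% | 69.7% → 70.6% |
| 23 | 28 | 23.9 | 83.5% → 85.8% | 69.7% → 71.6% |

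A simulation of 2,000,000 survival times per median agreed with the formula.

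**Two yardsticks.** Against a clock started at SBRT, the excess in the median is the wait itself if all patients wait equally long, whatever the survival distribution. Against an analysis of all registered patients, the excess is the factor 1/S(W) and depends only on deaths during the wait. With a 13.9-month median, the expected number of such deaths among 20 registered patients is 20 × (1 − S(W)) = 0.45 at 14 days and 0.90 at 28 days. Under a constant hazard the two comparisons give the same answer.

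**Sampling error.** At N = 20 without censoring, the 95% half-width for 12-month survival is 1.96 × √(0.55 × 0.45/20) = 0.218. Over the three medians it is 20-22 points.

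**The case against.** The strongest reply is that the effect hardly matters here. These are descriptive secondary endpoints in a 20-patient feasibility study, whose decision rests on accrual, toxicity, treatment delay and completion of therapy. Sampling error is several times the bias. Eligibility requires a life expectancy above 3 months (Synopsis), so early deaths should be rarer than a constant hazard implies. If nobody dies or drops out during the wait, analysing all registered patients would give the same result. All of this stands, and it limits the importance of the point. It does not remove the mismatch: more patients would not shrink the bias, and a confidence interval would not show it. Section XIII does time duration of response from treatment, but that does not cover overall survival.

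Three stronger readings are tempting but not supported:

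- *A 45-day wait.* A reader might take it from Appendix I, footnote 8: "Pre-SBRT procedures should be completed within 45 days of beginning treatment". That is a window for procedures, some of which (fiducial placement, for example) may precede enrolment. It does not measure registration to SBRT. The chemotherapy break implies at most about 4 weeks if registration follows the last dose.
- *Exclusions after surgery.* The evaluable-set sentence also mentions confirmation by central review. A reader might infer that patients found metastatic at exploration could be dropped later, and size this from the 11 of 36 patients in the tissue-factor series in Section XI. Sections V and IX describe a multidisciplinary review before treatment, and nothing re-judges eligibility after surgery. That series is a tumour-bank plasma cohort, not described as restaged after 3-4 months of chemotherapy. The review wording need not be deleted.
- *All three endpoints event-free by construction.* This is strict only for death. A patient found metastatic at planning is arguably a screen failure, and some local growth would not stop SBRT.

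**Conclusion.** The mismatch between time origin and analysis set is real, and the plan contains nothing that corrects it. Overall survival is biased upward, and both recurrence endpoints lean the same way. For a 2-4 week wait the excess in median survival is about 0.5-0.9 month. With medians from 8 to 23 months, 12-month survival is overstated by about 1 to 3 points and 6-month survival by about 1 to 5 points.

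These sizes rest on an assumed wait common to all patients, registration after the last chemotherapy dose, a constant hazard, and background medians from other populations. They apply to overall survival. The recurrence endpoints were not sized, because the documents give no suitable rates for a cohort going to resection.

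The bias is small against sampling error and touches no stopping or go/no-go rule. It is worth correcting because it is systematic and cheap to remove, and because the trial is meant to inform a phase II study.

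**What to change.** In Section IX, choose one pairing of clock and population for all three endpoints:

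1. Start the clock at the first SBRT fraction and analyse patients who began SBRT. This fits the stated objective and the post-radiation visit schedule, and is the simpler choice.
2. Keep the registration clock and analyse every registered eligible patient, whether or not SBRT was started. The text should then say how metastases found between registration and SBRT are counted. Otherwise the distant-recurrence endpoint keeps the same gap.

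In either case, report the distribution of the registration-to-SBRT interval and the number of registered patients who never started, with reasons.

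The cost is a wording change. Radiation dates are on the data list in Section X and registration is logged in the study database. Section VI already has patients who leave the study followed for survival, which helps option 2. Reported times under option 1 will be slightly shorter. No treatment or visit changes.
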